# 19.1.4. Pharmacodynamic/Biomarkers Figures and Tables

# **Figures**

No.	Population	IDSL / TST ID / Example Shell	Title	Programming Notes	Deliverable [Priority]
12.1	PD	PKONE, PKCF1	Individual Serum HER3 Concentration-Time plots (Linear and Semi-log)		SAC
12.2	PD		Box plot of Serum HER3 data by Dose Cohort	arenv/arprod/gsk263677 1/p3b115717/sac/drivers /f_pkp_box_single.sas	SAC

## Tables

No.	Population	IDSL / TST ID / Example Shell	Title	Programming Notes	Deliverable [Priority]
12.1	PD	PD1/Shell	Summary of Serum HER3 Data by Dose Cohort		SAC
12.2	PD	PD1/Shell	Summary of Change from Baseline of Serum HER3 Data by Dose Cohort		
12.3	PD	PD1/Shell	Summary of CD marker Data (%) by Dose Cohort		SAC
12.4	PD	PD1/Shell	Summary of CD marker Data (cells/cumm) by Dose Cohort		SAC
12.5	PD	Non-standard	Listing of Biomarker Data	by subjid, visit, bicat, bimeth, biorres in BIOMARK dataset	SAC
12.6	PD	PD10/Shell	Listing of Serum HER3 Data		SAC
12.7	PD	PD10/Shell	Listing of CD Marker Data		SAC

# 19.1.5. Pharmacokinetic Figures and Tables

# **Figures**

Figure No.	Population	IDSL No. / Example Shell	Title	Programming Notes	Deliverable Priority
13.1	PK parameter	PK16a, pkcf1p	Individual Plasma GSK2849330 Concentration-Time Plots by Dose Cohort in Part 1 (Linear and Semi-log)		SAC
13.2	PK parameter	РК17, РКСF2	Mean (± SD) GSK2849330 Plasma Concentration-Time Plots by Dose Cohort in Part 1 (Linear and Semi-log)		SAC
13.3	PK parameter	PK18, pkcf3	Median GSK2849330 Plasma Concentration-Time Plots by Dose in Part 1 (Linear and Semi-log)		SAC
13.4	PK parameter		Individual and Box Plot of Dose-Normalized Plasma GSK2636771 PK Parameters by Dose Cohort in Part 1	For Cmax, AUC(0-∞), AUC(0-168), and AUC(0-т) arenv/arprod/gsk263 6771/p3b115717/sac /drivers/f_pkp_box_s ingle.sas	SAC
13.5	PK parameter		Individual and Box Plot of Plasma GSK2636771 Pre-Dose Concentration Data on Day 8, 15 and 29 by Dose Cohort in Part 1	arenv/arprod/gsk263 6771/p3b115717/sac /drivers/f_pkc_box_p re.sas	SAC

### Tables

No.	Population	IDSL No. / Example Shell	Title	Programming Notes	Deliverabl e Priority
13.1	РК	PK01,	Summary of GSK2849330 Plasma Concentration-Time data by		SAC
	parameter	pkct1	Dose		SAC
13.2	РК	PKPT2	Summary of Derived Plasma GSK2849330 Pharmacokinetic		SAC
	parameter	FKFIZ	Parameters by Dose		SAC
13.3	PK Conc.	PKCl1P	Listing of Plasma GSK2849330 PK Concentration-Time Data	By part and original dose cohort	SAC
13.4	PK Parameter	PKPL1P	Listing of Plasma GSK2849330 PK Parameters Data		SAC

# 19.1.6. Immunogenicity

# Tables

No.	Populatio n	IDSL / TST ID / Example Shell	Title	Programming Notes	Deliverable [Priority]
14.1	All Treated	Shell	Summary of Immunogenicity of Anti-GSK2849330 Antibody Results	Only output data when IGSCATCD=2 (confirmed results)	SAC
14.2	All Treated	Shell	Listing of Anti-GSK2849330 Antibody Results	Output records for subjects with IGSCATCD=2 and IGSORRSCD=1; See details in shell	SAC
14.3	All Treated	Non-standard	Listing of Immunogenicity Sample Accountabilities	All information	SAC

# 19.1.7. ICH Listings

Table No	Population	IDSL No. / Example Shell	Title	Additional Programming Notes	Deliverable Priority
Study F	Population				
1	All Treated	TA1	Listing of Planned and Actual Treatments		SAC
2	All Treated	ES2	Listing of End of Study Records	Including all subjects; add a column of 'Complete study' with values of 'Yes' or 'No'; change column title of 'Date of Withdrawal' to 'Date of Disposition';	SAC
3	All Treated	IE3	Listing of Subjects with Inclusion/Exclusion Criteria Deviations		SAC
4	All Treated	DV2	Listing of Protocol Deviations		SAC
5	All Treated	DM2	Listing of Demographic characteristics		SAC
6	All Treated	DM9	Listing of Race		SAC
7	All Treated	DC2	Listings of Disease Characteristics at Initial Diagnosis		SAC
8	All Treated	MH2	Listing of Medical Conditions for All Subjects		SAC
9	All Treated	AC6	Listing of Prior Anti-Cancer Chemotherapy, Hormanal, Immunotherapy, Small Molecule Targeted Therapy, and Biologic Therapy		SAC
10	All Treated	AC7	Listing of Prior Anti-Cancer Radiation Therapy		SAC
11	All Treated		Listing of Prior Cancer Related Surgical Procedures	arenv/arprod/gsk2636771/p3b115717/ sac/drivers/l_surgery.sas	SAC
12	All Treated	CP_CM3	Listing of Concomitant Medications by Generic Term		SAC
Safety					
13	All Treated	OEX3a	Listing of Exposure to GSK2849330		SAC

Table No	Population	IDSL No. / Example Shell	Title	Additional Programming Notes	Deliverable Priority
14	All Treated		Listing of Exposure to Investigational Product	arenv/arprod/gsk2636771/p3b11 5717/sac/drivers/I_exp.sas	SAC
15	All Treated		Listing of Dose Reduction	arenv/arprod/gsk2636771/p3b11 5717/sac/drivers/I_exp_reductn.s as	SAC
16	All Treated		Listing of Dose Delay/Interruption	arenv/arprod/gsk2636771/p3b11 5717/sac/drivers/I_exp_intrup.sas	SAC
17	All Treated		Listing of Dose Escalation	arenv/arprod/gsk2636771/p3b1157 17/sac/drivers/l_exp_escal.sas	SAC
18	All treated	AE2	Relationship between System Organ Class and Verbatim Text		SAC
19	All Treated	OAE03	Listing of Subject Numbers for Individual Adverse Events		SAC
20	All Treated	AE8	Listing of All Adverse Events		SAC
21	All Treated	AE8	Listing of All Drug-Related Adverse Events		SAC
22	All Treated	AE8	Listing of All Serious Adverse Events		SAC
23	All treated	AE8	Listing of Adverse Events of Special Interest	See RAP Section 12.3	SAC
24	All treated		Listing of Liver Event Information for RUCAM Score	arenv/arprod/gsk2636771/p3b11 5717/sac/drivers/I_rucam.sas	SAC
25	All Treated	OLB7	Listing of Chemistry Laboratory Data		
26	All Treated	OLB7	Listing of Haematology Laboratory Data		SAC
27	All Treated	OLB7	Listing of Urine Laboratory Data		SAC
28	All Treated	OLB7	Listing of Coagulation and Other Laboratory Data		SAC
29	All treated	OLB7	Listing of Subjects with Grade 3 or Higher Toxicity in Clinical Chemistry Data		SAC
30	All treated	OLB7	Listing of Subjects with Grade 3 or Higher Toxicity in Haemetology Data		SAC

Table No	Population	IDSL No. / Example Shell	Title	Additional Programming Notes	Deliverable Priority
31	All treated	OLB7	Listing of Subjects with Grade 3 or Higher Toxicity in Urinalysis Data		SAC
32	All treated		Listing of Subjects with Grade 3 or Higher Toxicity in Liver Function Test	arenv/arprod/gsk2256098/fak11474 6/sac/drivers/l_lft8.sas	SAC

No.	Population	IDSL / TST ID / Example Shell	Title	Programming Notes	Deliverable [Priority]
1	All Treated	Non-standard	Listing of Randomisation	All information in RANDALL	SAC
2	All Treated	Non-standard	Listing of Substance Use	Including last date, type, history, average unit etc. in SUBUSE	SAC
3	All treated		Listing of Liver Event Information for RUCAM Score	arenv/arprod/gsk2636771/p3 b115717/sac/drivers/l_rucam .sas	SAC
4	All treated	LB13	Listing of Reference Ranges for Clinical Laboratory Tests		SAC
5	All Treated	EG3	Listing of ECG Interval Data		SAC
6	All Treated	CP_EG5	Listing of Subjects with Clinical Significant Abnormal ECG findings		SAC
7	All Treated	OECG5A	Listing of Fridericia's QTc Values greater than 501		SAC
8	All Treated	OVT7A	Listing of All Vital Signs		SAC
9	All Treated	OLVEF2A	Listing of Echocardiogram Results		SAC
10	All Treated	PS5A	Listing of ECOG Performance Status		SAC
11	All Treated	Non-standard	Listing of Biomarkers in Screening	Including test methods, tests, results in BIOMARK	SAC
12	PGx	Non-standard	Listing of Pharmacogenetic sample accountability	All information in GENPRO	

### **19.2.** Data Display Specifications (Example Shells)

Protocol : HER117158 Population : All Treated Page x of n

#### Table x.x Summary of number of subjects with positive immunogenicity results by visit (Safety population)

Sampling Time Point	Cohort 1	Cohort 2	Cohort 3	Cohort X
	(N=X)	(N=X)	(N=X)	(N=X)
Week 0 (Baseline)	x/x (xx%)	x/x (xx%)	x/x (xx%)	x/x (xx%)
Week X	x/x (xx%)	x/x (xx%)	x/x (xx%)	x/x (xx%)
Any visit post-baseline	x/x (xx%)	x/x (xx%)	x/x (xx%)	x/x (xx%)

Note: This listing includes all subjects tested positive for anti-GSK2849330 antibody in confirmatory testing at any time during the study.

Percentages are calculated specific for each treatment arm and each sampling time point.

The denominator is the total number of subjects tested for anti-GSK2849330 antibody, and the numerator is the number of subjects tested positive for anti-GSK2849330 antibody in confirmatory testing.

HER117158

Page x of n

Protocol : HER117158 Population : All Treated

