2.2. Part 2: Molecularly Defined Tumor Histology Groups

Objective	Endpoint
Primary	

 To evaluate the safety of GSK2849330 in a larger population of subjects in molecularly-defined tumor histology groups at the dose regimen(s) recommended for further exploration in Part 1. 	
 AEs, SAEs, DLTs, and changes in laboratory values, ECGs, and vital signs.
Secondary	

 To evaluate preliminary evidence of clinical benefit. To further characterize target engagement and PD effects of GSK2849330. To further characterize the PK of GSK2849330. To characterize the relationship between GSK2849330 PK, markers of target engagement, and/or PD markers. To evaluate the immunogenicity of GSK2849330 following IV administration. 	
 ORR, tumor markers, and other measures of clinical benefit. Total and phospho-HER3 from tumor tissue. PK parameter values for GSK2849330. PK parameter values for GSK2849330 Antibodies to GSK2849330 in serum
Exploratory	

 To explore additional measures of clinical benefit. To further characterize target engagement and PD effects of GSK2849330. To explore relationship between pre-treatment HER3 or HER3/NRG1 expression levels and clinical outcome. 	
 Progression free survival (PFS), ORR according to immune-related response criteria (irRc) and modified Response Evaluation Criteria in Solid Tumors mRECIST where applicable, and other tumor markers and measures of clinical benefit Pre- and post- treatment biomarkers (cells, proteins, RNA and/or DNA) from circulation and/or tumor tissue. Pre-treatment HER3 expression or HER3 and NRG1 levels, efficacy outcome parameters.

 To identify molecular features potentially predictive of response to GSK2849330. 	
 Prediction analysis of biomarkers (cells, DNA, RNA or protein) in tumor, and/or circulation with efficacy endpoints.

Objective	Endpoint
Pharmacogenetic (PGx) Exploratory	

 To investigate the relationship between genetic variants in candidate genes and safety, tolerability, PK, PD, and/or efficacy of GSK2849330. 	
 Genetic variations in selected candidate genes, such as the FCγ receptor family, safety, tolerability, PK, PD, and/or efficacy endpoints.

[figure not shown]

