13.7.4. Immunogenicity Analyses

The immunogenicity assessment will include the incidence (confirmed positive results only) and titers of anti-GSK2849330 binding antibodies at any time point post baseline. Full details will be provided in the RAP.

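### The immunogenicity summary does not separate treatment-induced antibody from antibody already present before dosing

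*SAP*

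**What the plan says.** Evaluating immunogenicity is a secondary objective in both parts (Protocol 2.1 and 2.2): "To evaluate the immunogenicity of GSK2849330 following IV administration". Protocol 13.7.4 sets out the analysis: "The immunogenicity assessment will include the incidence (confirmed positive results only) and titers of anti-GSK2849330 binding antibodies at any time point post baseline". It leaves the details to the RAP, which is the SAP reviewed here.

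The SAP plans one summary, Table 14.1 (Section 19.1.6). Its programming note restricts the output to confirmed results. The shell in Section 19.2 has a baseline row, a row per visit, and a cumulative row labelled "Any visit post-baseline". The counting rule is the same in every row. For the top of the fraction, the shell's note says that "the numerator is the number of subjects tested positive for anti-GSK2849330 antibody in confirmatory testing". For the bottom, it makes no exception for those already positive before dosing: "The denominator is the total number of subjects tested for anti-GSK2849330 antibody". A further note sets the level at which this is done: "Percentages are calculated specific for each treatment arm and each sampling time point".

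SAP Section 15 and the listing shell in Section 19.2 add a by-subject listing for antibody-positive subjects. It shows sampling time, screening result, confirmatory result and titer. Neither document defines treatment-induced or treatment-boosted antibody.

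**The concern.** The objective concerns antibody formed after dosing, and the protocol calls the result an incidence. The cumulative row nevertheless counts a subject who was already positive on Day 1 before the infusion, provided a later sample is also confirmed positive.

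The baseline row does not cure this, because the rows are marginal counts. One baseline positive and three post-baseline positives are compatible with three converters (the baseline positive later tested negative) or with two converters plus one persistent positive. The summary cannot tell these apart.

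Elsewhere the SAP does make the distinction. Adverse events are treatment-emergent if they start or worsen after first dose (Section 12.2), and serum HER3 has a defined pre-dose baseline with a change-from-baseline table (Section 14.1). The antibody summary has no counterpart. At stake is a secondary safety-related percentage in small columns, where one subject moves the figure visibly.

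**Working it through.** The documents state no immunogenicity rate, sample size or power, so there is no planned figure to reproduce. The check is what the counting rule does.

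**Inputs from the documents**
- Numerator and denominator: SAP 19.2 table shell, as quoted.
- Column sizes: Protocol Table 3 plans at least 3 escalation subjects plus up to 3 PK/PD subjects per dose level after the first. SAP 7.1 combines subjects with the same dose and frequency, so a typical Part 1 column is 3 + 3 = 6. SAP 7.1 also pools Part 2 into one 30 mg/kg column. Protocol 5.1 plans at least 12 and at most about 30 subjects in each of four groups, so 48 to 120 in that column.
- Samples: a Day 1 pre-dose sample is scheduled in all of Protocol Tables 7 to 12. In Tables 8 to 12 the only scheduled later samples are at the Follow-up and Post-study visits.

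**Assumed, because not in the documents**
- b, the share positive at baseline: 0%, 2%, 5%, 10%.
- t, the conversion rate among baseline negatives: 5%, 10%.
- s, the share of baseline positives still confirmed positive later: 1, with no boosting.

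**Expected rates**
Cumulative row = b·s + (1 − b)·t. Treatment-induced incidence among baseline negatives = t. Difference = b·(s − t).

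| b | Row, t = 5% | Difference | Row, t = 10% | Difference |
|---|---|---|---|---|
| 0% | 5.0% | 0 | 10.0% | 0 |
| 2% | 6.9% | 1.9 points | 11.8% | 1.8 points |
| 5% | 9.75% | 4.75 points | 14.5% | 4.5 points |
| 10% | 14.5% | 9.5 points | 19.0% | 9.0 points |

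Persistence matters. If no baseline positive stayed positive (s = 0), the difference would be −b·t, a slight understatement. For b = t = 10% that is −1 point.

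**Counts in one column**
With n subjects tested, k persistent baseline positives and c converters, the row gives (k + c)/n and the treatment-induced rate is c/(n − k). Each persistent baseline positive adds 1/n to the row.
- Part 1 column of 6: 1/6 = 16.7 points. With one such subject and one converter, the row gives 2/6 = 33.3% against 1/5 = 20.0%.
- Pooled Part 2 column at planned size: 1/48 = 2.1 points down to 1/120 = 0.8 points.

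**Chance that the issue arises at all**
P(at least one baseline positive) = 1 − (1 − b)^N. For the 34 subjects planned in Part 1 this is 49.7%, 82.5% and 97.2% at b = 2%, 5% and 10%.

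**Denominator**
The shell does not say whether a subject with only a pre-dose sample counts as tested in the cumulative row. Where later samples come only after the last dose, a subject lost before then has no post-baseline result. If one of 6 is such a subject and one converts, the row reads 1/6 = 16.7% or 1/5 = 20.0%, depending on the reading.

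**The case against.** A reader might infer that the table misreports drug-induced incidence as a matter of fact. The documents do not support that. The row is not labelled drug-induced or treatment-emergent, the shell is titled as a count of positive results by visit, and it implements Protocol 13.7.4 faithfully. There is no conflict between protocol and SAP. Nor does pre-dose reactivity put a subject in the cumulative row automatically, since a later sample must also be confirmed positive. With no prevalence given, overstatement is conditional.

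A reader might also size the effect by Part 2 histology group, taking 1/12 = 8.3 or 1/30 = 3.3 points. SAP 7.1 plans no such columns.

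Pre-existing antibody is also partly disclosed. If the baseline row is zero the question disappears. If not, the listing lets a reader sort subjects one by one, which may be thought enough for small descriptive cohorts. Finally, a boosted category needs a titer threshold that neither document provides.

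All of this stands, and it limits the point to a conditional one of low severity. It does not remove it. The protocol delegated the detail to the SAP, the SAP supplies no definition, and sorting a listing after the fact is not a pre-specified summary of a secondary objective.

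**Conclusion.** The immunogenicity summary counts every confirmed post-baseline positive over all subjects tested and does not cross-classify by baseline status. If any subject is positive before dosing and stays positive without boosting, the cumulative row overstates treatment-induced incidence. Over the assumed range (b = 2% to 10%, t = 5% to 10%, s = 1) the expected excess is 1.8 to 9.5 points. It is zero if nobody is positive at baseline.

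These sizes rest on assumed prevalence, conversion and persistence, and on planned column sizes. SAP Section 11 says the study stopped early, so actual columns may be smaller and one subject's weight larger. The documents do not show that any reported incidence will be wrong. They show that the planned table could not tell whether it is.

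**What to change.** Keep the present rows and the listing. In SAP Section 15 and the Table 14.1 shell, add:

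- Treatment-induced: baseline-negative subjects later confirmed positive, over baseline-negative subjects with at least one post-baseline sample.
- Treatment-boosted: baseline-positive subjects whose titer rises by more than a threshold pre-specified from assay validation, over baseline-positive subjects with at least one post-baseline sample.
- A footnote stating that the denominator of the cumulative post-baseline row is subjects with at least one post-baseline sample.

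The cost is a few table rows and one pre-specified titer threshold. The Day 1 pre-dose samples and the titers of confirmed positives are already planned, so no new sampling is needed.

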### Listing x.x Listing of Immunogenicity Results For Anti-GSK2849330 Positive Subjects

	GSK2849330			Anti-0	GSK2849330 An	tibody
Inv./	Dose/Dose Interval	Sampling	Date of	Screening	Confirming	
Subj.		Time Point	Sampling	Result	Result	Titer
xxxxx/ xxxxxx	xx/xx	*****	DDMMMYYYY	Neg		
		XXXXXXXXXX	DDMMMYYYY	Pos	Pos	XX
		XXXXXXXXXX	DDMMMYYYY	Pos	Pos	XX

Note:

1. Move column 'GSK2849330 Dose/Dose Interval' to first column and change it to Treatment, i.e. "Part 1 Cohort: 3 mg/kg weekly".

2. Add "GSK2849330 Conc. (μg/mL)" as last column with value of pre-dose PK Conc. merged by VISIT for this listing.

3. Add 'Study Day' in column of 'Date of Sampling'.

### Example PD1 Protocol: HER117158 Population: PD Population

CD Markers	Treatment	N	Planned Relative Time	n	Mean	SD	Median	Min.	Max.
CD 45					mean				
	Part 1 Cohort: 1.4 mg/kg weekly	24	Pre-dose	24	NQ		NQ	NQ	хххх
			30m	24	xxxx.xx	xx.xx	xxxx.x	xxxx	хххх
			1h	23	xxxx.xx	xx.xx	xxxx.x	xxxx	xxxx
			2h	24	xxxx.xx	xx.xx	xxxx.x	XXXX	XXXX
	Part 1 Cohort: 3 mg/kg every 2 weeks	24	Pre-dose	24	xxxx.xx	xx.xx	XXXX.X	хххх	хххх
			30m	21	xxxx.xx	xx.xx	xxxx.x	xxxx	хххх
			1h	21	xxxx.xx	xx.xx	xxxx.x	xxxx	xxxx
			2h	21	xxxx.xx	xx.xx	xxxx.x	xxxx	xxxx

# Table 2Summary of CD Marker Data (%) by Dose Cohort

USER ID: directory/program.sas 01JAN2002 12:01

Page 1 of 1

### Example PD1 Protocol: HER117158 Population: PD Population

Treatment	N	Planned Relative Time	n	Mean	SD	Median	Min.	Max.
Part 1 Cohort: 1.4 mg/kg weekly	24	Pre-dose	24	NQ		NQ	NQ	хххх
		30m	24	xxxx.xx	xx.xx	xxxx.x	xxxx	xxxx
		1h	23	xxxx.xx	xx.xx	xxxx.x	xxxx	xxxx
		2h	24	xxxx.xx	xx.xx	xxxx.x	XXXX	XXXX
Part 1 Cohort: 3 mg/kg every 2 weeks	24	Pre-dose	24	xxxx.xx	XX.XX	XXXX.X	хххх	хххх
		30m	21	xxxx.xx	xx.xx	xxxx.x	xxxx	хххх
		1h	21	XXXX.XX	XX.XX	xxxx.x	XXXX	XXXX
		2h	21	xxxx.xx	xx.xx	xxxx.x	XXXX	XXXX

# Table 1Summary of Serum HER3 Data by Dose Cohort

USER ID: directory/program.sas 01JAN2002 12:01

Page 1 of 1

### Example PD1 Protocol: HER117158 Population: PD Population

		Planned						
Treatment	Ν	Relative Time	n	Mean	SD	Median	Min.	Max.
Part 1 Cohort: 1.4 mg/kg weekly	24	30m	24	XXXX.XX	xx.xx	xxxx.x	хххх	хххх
		1h 2h	23 24	xxxx.xx xxxx.xx	xx.xx xx.xx	xxxx.x xxxx.x	xxxx xxxx	xxxx xxxx
Part 1 Cohort: 3 mg/kg every 2 weeks	24	30m	24	XXXX.XX	xx.xx	xxxx.x	хххх	хххх
		1h 2h	21 21	xxxx.xx xxxx.xx	xx.xx xx.xx	xxxx.x xxxx.x	xxxx xxxx	xxxx xxxx

# Table 1 Summary of Change from Baseline value of Serum HER3 Data by Dose Cohort

Page 1 of 1

### HER117158

### Example PD10 Protocol: HER117158 Population: PD Population

Table 2 Listing of Serum HER3 Concentration-Time Data

Treatment	Inv./ Subj.	VISIT	Date	Actual Time	Planned Relative Time	Concentration (unit)	PK Concentration (unit)
Part 1 Cohort: 1.4 mg/kg weekly	PPD	Day 1	01JAN2003	08:55	Pre-dose	NQ (<0.23)	
			01JAN2003	10:05	1h	xxxx	
			01JAN2003	11:00	2h	хххх	
			07JAN2003	08:55	Pre-dose	xxxx	
			07JAN2003	10:00	1h	XXXX	
			07JAN2003	10:59	2h	хххх	
Part 1 Cohort: 3 mg/kg every 2 weeks			01JAN2003	08:55	Pre-dose	хххх	
			01JAN2003 01JAN2003	10:05 11:00	1h 2h	xxxx NR	

USER ID: directory/program.sas 01JAN2002 12:01
